Appendix 9 EuroQol 5-Dimension, 5-Level Questionnaire (cont.)

- We would like to know how good or bad your health is TODAY.
- This scale is numbered from 0 to 100.
- 100 means the best health you can imagine.
0 means the worst health you can imagine.
- Mark an X on the scale to indicate how your health is TODAY.
- Now, please write the number you marked on the scale in the box below.

YOUR HEALTH TODAY =

The best health
you can imagine

The worst health
you can imagine

Appendix 10 Management of Cobimetinib plus Atezolizumab-Associated Adverse Events (Arm A)

Note: For information regarding management of atezolizumab-associated adverse events, please refer to [Appendix 11](#).

Guidelines for Management of Cobimetinib plus Atezolizumab Adverse Events

Event	Action to Be Taken
General guidance for dose modifications and treatment delays and discontinuation	
 • There will be no dose modifications for atezolizumab. • If atezolizumab is withheld and corticosteroids are initiated for an atezolizumab-related toxicity, corticosteroids must be tapered over ≥ 1 month to ≤ 10 mg/day oral prednisone or equivalent before atezolizumab can be resumed.^{a, b, c} 
The dose of cobimetinib can be reduced by 20 mg (one dose level) up to two times (i.e., from 60 mg to 40 mg and then from 40 mg to 20 mg). If further dose reduction is indicated after two dose reductions, the patient must discontinue cobimetinib but may continue treatment with atezolizumab at the investigator's discretion.
 
 • If cobimetinib is withheld for > 28 days because of toxicity, the patient should be discontinued from cobimetinib, unless resumption of treatment is approved by the Medical Monitor after discussion with the investigator. • After dose reduction, consideration may be given to allow for dose escalation of cobimetinib by a maximum of one dose level following resolution of the adverse event that resulted in dose modification, provided there are no safety concerns. • If atezolizumab is withheld for > 12 weeks because of toxicity, the patient should be discontinued from atezolizumab, unless resumption of treatment is approved by the Medical Monitor after discussion with the investigator.
IRRs, CRS, anaphylaxis, and hypersensitivity reaction	
 • Guidelines for management of IRRs and CRS are provided in the Atezolizumab Investigator's Brochure and Appendix 11 • For anaphylaxis precautions, see Appendix 7. • For severe hypersensitivity reactions, permanently discontinue all study treatment.

CRS = *cytokine-release syndrome*; IRR = infusion-related reaction.

^a If corticosteroids have been initiated, they must be tapered over ≥ 1 month to ≤ 10 mg/day oral prednisone or equivalent before atezolizumab can be resumed.

^b Atezolizumab may be withheld for a period of time beyond 105 days to allow for corticosteroids to be reduced to ≤ 10 mg/day oral prednisone or equivalent. The acceptable length of the extended period of time must be agreed upon by the investigator and the Medical Monitor.

^c Resumption of atezolizumab may be considered in patients who are deriving benefit and have fully recovered from the immune-mediated event. Patients can be rechallenged with atezolizumab only after approval has been documented by both the investigator (or an appropriate delegate) and the Medical Monitor.

Appendix 10

Management of Cobimetinib plus Atezolizumab-Associated Adverse Events (Arm A) (cont.)

GASTROINTESTINAL TOXICITY

Diarrhea and colitis have been associated with the administration of cobimetinib plus atezolizumab (see Section [5.1.1.3.2](#)).

See [Table 1](#) for guidelines on how to manage gastrointestinal toxicity in patients treated with cobimetinib plus atezolizumab.

Appendix 10 Management of Cobimetinib plus Atezolizumab-Associated Adverse Events (Arm A) (cont.)

Table 1 Guidelines for Managing Atezolizumab- and Cobimetinib-Associated Gastrointestinal Toxicity

Event	Action to Be Taken
Gastrointestinal toxicity	
Gastrointestinal events: general guidance	
 • All events of diarrhea or colitis should be thoroughly evaluated for more common etiologies other than drug-induced effects. • For events of significant duration or severity or associated with signs of systemic inflammation or acute-phase reactants, check for immune-mediated colitis. • Administer anti-diarrheal agents and other maximal supportive care per institutional guidelines, such as at the first report of watery diarrhea or loose stool, initiate maximal anti-diarrheal supportive care (Lomotil[®] and loperamide). • Suggested regimen: 
 – Loperamide: Initiate dose with 4 mg, then 4 mg/6 hr around the clock, alternating with Lomotil.[®] – Lomotil[®] (diphenoxylate and atropine): Dispense 2 tablets (diphenoxylate 5 mg, atropine 0.05 mg) every 6 hours around the clock. – Continue Lomotil[®] and loperamide until no loose stools for 24 hours. – If Grade ≤ 2 diarrhea persists after 48 hours of total treatment with Lomotil[®] and loperamide, consider second-line agents (e.g., octreotide, budesonide, tincture of opium). • Oral supplementation: 
 – Initiate oral supplementation of potassium and/or magnesium if serum levels are $< LLN$. – Consider oral rehydration therapy (e.g., Pedialyte[®]) for Grade ≥ 1 diarrhea or vomiting. • Dietary modifications: 
 – Stop all lactose-containing products and instruct patient to eat small meals. – Suggest the BRAT diet (banana, rice, apples, toast) diet, without fiber (other vegetables and fruits). – Encourage adequate hydration with salt-containing liquids, such as broth or Gatorade[®].
Diarrhea, Grade 1 or Grade 2 (tolerable)	
 • Continue atezolizumab and cobimetinib. • Investigate etiology, referring patient to GI specialist for evaluation of possible colitis if appropriate. • Initiate supportive care and monitor patient closely.

Appendix 10 Management of Cobimetinib plus Atezolizumab-Associated Adverse Events (Arm A) (cont.)

Table 1 Guidelines for Managing Atezolizumab- and Cobimetinib-Associated Gastrointestinal Toxicity (cont.)

Event	Action to Be Taken
Diarrhea, Grade 2 (intolerable) or Grade 3	
 • Withhold atezolizumab and cobimetinib. • Initiate supportive care and monitor patient closely. • Discontinue medications that may exacerbate colitis (e.g., NSAIDs) while investigating etiology. • Investigate etiology and refer patient to GI specialist for evaluation of possible colitis, including biopsy if appropriate. • If event resolves to Grade 1 or better within 12 weeks, resume atezolizumab at fixed dose. If not, permanently discontinue atezolizumab and cobimetinib. ^{a, b, c} • If event resolves to Grade 1 or better within 28 days, resume cobimetinib with the dose reduced by one level. If not, permanently discontinue cobimetinib.
Diarrhea, Grade 4	
 • Permanently discontinue atezolizumab and cobimetinib, and contact Medical Monitor. ^c • Initiate supportive care and monitor patient closely. • Discontinue medications that may exacerbate colitis (e.g., NSAIDs) while investigating etiology. • Rule out bowel perforation. • Investigate etiology, referring patient to GI specialist for evaluation of possible colitis, including biopsy if appropriate.
Colitis, Grade 1	
 • Continue atezolizumab and cobimetinib. • Initiate supportive care and monitor patient closely. • Discontinue medications that may exacerbate colitis (e.g., NSAIDs). • Refer patient to GI specialist for evaluation and confirmatory biopsy if symptoms persist for > 7 days.
Colitis, Grade 2	
 • Withhold atezolizumab and cobimetinib. • Initiate supportive care and monitor patient closely. • Discontinue medications that may exacerbate colitis (e.g., NSAIDs). • Refer patient to GI specialist for evaluation and confirmatory biopsy. • For recurrent events or events that persist >5 days, initiate treatment with 1–2 mg/kg/day oral prednisone or equivalent. • If event resolves to Grade 1 or better within 12 weeks, resume atezolizumab at fixed dose. If not, permanently discontinue atezolizumab and cobimetinib. ^{a, b, c} • If event resolves to Grade 1 or better within 28 days, resume cobimetinib with the dose reduced by one level. If not, permanently discontinue cobimetinib.

Appendix 10 Management of Cobimetinib plus Atezolizumab-Associated Adverse Events (Arm A) (cont.)

Table 1 Guidelines for Managing Atezolizumab- and Cobimetinib-Associated Gastrointestinal Toxicity (cont.)

Event	Action to Be Taken
Colitis, Grade 3	
 • Withhold atezolizumab and cobimetinib. • Initiate supportive care and monitor patient closely. • Discontinue medications that may exacerbate colitis (e.g., NSAIDs). • Refer patient to GI specialist for evaluation and confirmatory biopsy. • Initiate treatment with 1–2 mg/kg/day IV methylprednisolone or equivalent and convert to 1–2 mg/kg/day oral prednisone or equivalent upon improvement. • If event resolves to Grade 1 or better within 12 weeks, resume atezolizumab at fixed dose. If not, permanently discontinue atezolizumab and cobimetinib. ^{a, b, c} • If event resolves to Grade 1 or better within 28 days, resume cobimetinib with dose reduced by one level. If not, permanently discontinue cobimetinib.
Colitis, Grade 4	
 • Permanently discontinue atezolizumab and cobimetinib, and contact Medical Monitor. ^c • Initiate supportive care and monitor patient closely. • Discontinue medications that may exacerbate colitis (e.g., NSAIDs). • Refer patient to GI specialist for evaluation and confirmatory biopsy. • Initiate treatment with 1–2 mg/kg/day IV methylprednisolone or equivalent and convert to 1–2 mg/kg/day oral prednisone or equivalent upon improvement. • If event does not improve within 48 hours after initiating corticosteroids, consider adding an immunosuppressive agent. • If event resolves to Grade 1 or better, taper corticosteroids over ≥ 1 month.

GI=gastrointestinal; NSAID=non-steroidal anti-inflammatory drug.

- ^a If corticosteroids have been initiated, they must be tapered over ≥ 1 month to ≤ 10 mg/day oral prednisone or equivalent before atezolizumab can be resumed.
- ^b Atezolizumab may be withheld for a period of time beyond 105 days to allow for corticosteroids to be reduced to ≤ 10 mg/day oral prednisone or equivalent. The acceptable length of the extended period of time must be agreed upon by the investigator and the Medical Monitor.
- ^c Resumption of atezolizumab may be considered in patients who are deriving benefit and have fully recovered from the immune-mediated event. Patients can be rechallenged with atezolizumab only after approval has been documented by both the investigator (or an appropriate delegate) and the Medical Monitor.

Appendix 10 Management of Cobimetinib plus Atezolizumab-Associated Adverse Events (Arm A) (cont.)

HEPATOTOXICITY

Hepatotoxicity has been associated with the administration of atezolizumab and cobimetinib (see Section 5.1.1.2.1)

Patients with LFT abnormalities should be managed according to the guidelines in Table 2.

Table 2 Guidelines for Managing Atezolizumab and Cobimetinib–Associated Hepatotoxicity

Event	Action to Be Taken
Elevations in ALT, AST, and/or bilirubin	
AST/ALT > ULN to $\leq 3 \times$ ULN with total bilirubin < $2 \times$ ULN	
 • Continue atezolizumab and cobimetinib. • Continue with the standard monitoring plan (i.e., LFTs Q4W before dosing).
AST/ALT > $3 \times$ ULN to < $5 \times$ ULN with total bilirubin < $2 \times$ ULN	
 • Continue all study treatment. • Monitor LFTs at least weekly. • Consider referral to a hepatologist and liver biopsy. • For suspected immune-mediated events of > 5 days duration 
 – Consider withholding atezolizumab^c – Consider administering 1–2 mg/kg/day oral prednisone or equivalent followed by ≥ 1 month taper – Restart atezolizumab if event resolves to Grade 1 or better within 12 weeks^{a, b} – Permanently discontinue atezolizumab and cobimetinib if event does not resolve to Grade 1 or better within 12 weeks^{a, b, c}
AST/ALT > $5 \times$ ULN to < $10 \times$ ULN with total bilirubin < $2 \times$ ULN	
 • Continue all study treatment. • Monitor LFTs at least weekly. • Consider referral to a hepatologist and liver biopsy. • For suspected immune-mediated events: 
 – Withhold atezolizumab – Consider administering 1–2 mg/kg/day oral prednisone or equivalent followed by ≥ 1 month taper – If event does not improve within 48 hours after initiating corticosteroids, consider adding an immunosuppressive agent. If event resolves to Grade 1 or better, taper corticosteroids over ≥ 1 month. – Permanently discontinue atezolizumab and cobimetinib if event does not resolve to Grade 1 or better within 12 weeks^{a, b, c}

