5.1.5.3 Management of Cobimetinib- and Atezolizumab-Specific Adverse Events (Arm A)

Toxicities associated or possibly associated with cobimetinib plus atezolizumab treatment should be managed according to standard medical practice.

For management of cobimetinib- and atezolizumab-specific toxicities, including IRRs, gastrointestinal toxicity, dermatologic toxicity, hepatotoxicity, pulmonary toxicity, potential eye toxicity, reductions in LVEF from baseline, rhabdomyolysis, elevated CPK, and hemorrhage, see [Appendix 10](#).

Guidelines for management of patients who experience atezolizumab-associated or possibly associated adverse events, including infusion-related reactions and immune-mediated reactions (e.g., pulmonary, hepatic, gastrointestinal, endocrine, ocular, myocarditis, pancreatic, dermatologic, neurologic, meningoencephalitis, and renal events) are provided in [Appendix 11](#).

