- ^b If corticosteroids have been initiated, they must be tapered over ≥ 1 month to ≤ 10 mg/day oral prednisone or equivalent before atezolizumab can be resumed.
- ^c Resumption of atezolizumab may be considered in patients who are deriving benefit and have fully recovered from the immune-mediated event. Patients can be re-challenged with atezolizumab only after approval has been documented by both the investigator (or an appropriate delegate) and the Medical Monitor.

Appendix 11

Risks Associated with Atezolizumab and Guidelines for Management of Adverse Events Associated with Atezolizumab (cont.)

HEPATIC EVENTS

Immune-*mediated* hepatitis has been associated with the administration of atezolizumab. Eligible patients must have adequate liver function, as manifested by measurements of total bilirubin and hepatic transaminases, and liver function will be monitored throughout study treatment. Management guidelines for hepatic events are provided in [Table 2](#).

Patients with right upper-quadrant abdominal pain and/or unexplained nausea or vomiting should have liver function tests (LFTs) performed immediately and reviewed before administration of the next dose of study drug.

For patients with elevated LFTs, concurrent medication, viral hepatitis, and toxic or neoplastic etiologies should be considered and addressed, as appropriate.

Table 2 Management Guidelines for Hepatic Events

Event	Management
Hepatic event, Grade 1	
 • Continue atezolizumab. • Monitor LFTs until values resolve to within normal limits.
Hepatic event, Grade 2	
All events:
 
 • Monitor LFTs more frequently until return to baseline values. 
Events of > 5 days' duration:
 
 • Withhold atezolizumab for up to 12 weeks after event onset. ^a • Initiate treatment with 1–2 mg/kg/day oral prednisone or equivalent. • If event resolves to Grade 1 or better, resume atezolizumab. ^b • If event does not resolve to Grade 1 or better while withholding atezolizumab, permanently discontinue atezolizumab and contact Medical Monitor. ^c

LFT=liver function test.

^a Atezolizumab may be withheld for a longer period of time (i.e., > 12 weeks after event onset) to allow for corticosteroids (if initiated) to be reduced to ≤ 10 mg/day oral prednisone or equivalent. The acceptable length of the extended period of time must be agreed upon by the investigator and the Medical Monitor.

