^b If corticosteroids have been initiated, they must be tapered over ≥ 1 month to ≤ 10 mg/day oral prednisone or equivalent before atezolizumab can be resumed.

^c Resumption of atezolizumab may be considered in patients who are deriving benefit and have fully recovered from the immune-*mediated* event. Patients can be re-challenged with atezolizumab only after approval has been documented by both the investigator (or an appropriate delegate) and the Medical Monitor.

Appendix 11

Risks Associated with Atezolizumab and Guidelines for Management of Adverse Events Associated with Atezolizumab (cont.)

Table 2 Management Guidelines for Hepatic Events (cont.)

Event	Management
Hepatic event, Grade 3 or 4	
 • Permanently discontinue atezolizumab and contact Medical Monitor. ^c • Consider patient referral to gastrointestinal specialist for evaluation and liver biopsy to establish etiology of hepatic injury. • Initiate treatment with 1–2 mg/kg/day oral prednisone or equivalent. • If event does not improve within 48 hours after initiating corticosteroids, consider adding an immunosuppressive agent. • If event resolves to Grade 1 or better, taper corticosteroids over ≥ 1 month.

LFT = liver function test.

- ^a Atezolizumab may be withheld for a longer period of time (i.e., > 12 weeks after event onset) to allow for corticosteroids (if initiated) to be reduced to ≤ 10 mg/day oral prednisone or equivalent. The acceptable length of the extended period of time must be agreed upon by the investigator and the Medical Monitor.
- ^b If corticosteroids have been initiated, they must be tapered over ≥ 1 month to ≤ 10 mg/day oral prednisone or equivalent before atezolizumab can be resumed.
- ^c Resumption of atezolizumab may be considered in patients who are deriving benefit and have fully recovered from the immune-mediated event. Patients can be re-challenged with atezolizumab only after approval has been documented by both the investigator (or an appropriate delegate) and the Medical Monitor.

GASTROINTESTINAL EVENTS

Immune-mediated colitis has been associated with the administration of atezolizumab. Management guidelines for diarrhea or colitis are provided in [Table 3](#).

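### Arm A, suspected immune-mediated AST/ALT > 3 to < 5 × ULN for more than 5 days: Appendix 10 makes withholding atezolizumab optional, Appendix 11 directs it for Grade 2, and no text ranks the two

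*Protocol*

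**What the plan says.** Protocol Appendix 10, Table 2 has a row for AST/ALT > 3 to < 5 × ULN with total bilirubin < 2 × ULN. Its default is to carry on with all study treatment and check liver tests at least weekly. A sub-list opens "For suspected immune-mediated events of > 5 days duration". Under it come "Consider withholding atezolizumab", which carries footnote c on rechallenge; an optional course of prednisone; "Restart atezolizumab if event resolves to Grade 1 or better within 12 weeks"; and an instruction to stop both drugs for good if that has not happened within 12 weeks.

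Appendix 11, Table 2 is organised by grade. For a Grade 2 hepatic event of more than 5 days it says "Withhold atezolizumab for up to 12 weeks after event onset" and directs prednisone. For Grade 3 or 4 it says "Permanently discontinue atezolizumab and contact Medical Monitor".

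Section 5.1.5.3, headed for Arm A, refers to both appendices. Appendix 10 is named in a sentence that begins "For management of cobimetinib- and atezolizumab-specific toxicities, including IRRs, gastrointestinal toxicity, dermatologic toxicity, hepatotoxicity". Appendix 11 is named for "immune-mediated reactions (e.g., pulmonary, hepatic, gastrointestinal, endocrine, ocular, myocarditis, pancreatic, dermatologic" and other events.

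**The concern.** The same Arm A patient can fall under both tables, and the tables differ on whether to give the next atezolizumab dose. A site that opens Appendix 10 may keep dosing, every 2 weeks, through a liver event that it already suspects is immune-mediated and that has lasted more than 5 days. A site that opens Appendix 11 and grades the event as 2 would withhold. At stake are patient safety and uniform management within the arm, not the efficacy inference.

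**Working it through.** No design figure is involved, so the check is a comparison of texts.

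**1. What grade is the event?** The Appendix 10 row allows a restart once the event reaches Grade 1 or better. The row therefore treats the event as above Grade 1. The protocol grades by NCI CTCAE v4.0 but does not print the AST/ALT cut-offs, so the documents alone do not fix the grade further.

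**2. The two instructions side by side (suspected immune-mediated, more than 5 days).**

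| Item | Appendix 10, Table 2 (> 3 to < 5 × ULN, bilirubin < 2 × ULN) | Appendix 11, Table 2 (Grade 2) |
|---|---|---|
| Atezolizumab | Withholding optional | Withholding directed |
| Prednisone | Optional | Directed |
| Back to Grade 1 or better | Restart | Resume |
| Not resolved | Stop both drugs after 12 weeks | Stop atezolizumab |

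**3. Does any text rank them?**

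- Leaning to Appendix 10: Section 5.1 (use each arm's own guidelines), Section 5.1.1.2.1 (hepatotoxicity), Section 5.1.3 (overlapping toxicities, including hepatic) and the lead-in to Appendix 10, Table 2: "Patients with LFT abnormalities should be managed according to the guidelines in Table 2".
- Leaning to Appendix 11: the opening note of Appendix 10, which sends atezolizumab-associated events there.
- Naming both without ranking: Sections 4.3.2.2, 4.6.2 and 5.1.5.3.

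None is a precedence rule. Where Appendix 10 means to defer to Appendix 11 for atezolizumab it says so, as for Stevens-Johnson syndrome or toxic epidermal necrolysis (Table 3) and immune-mediated ocular toxicity (Table 5). The hepatotoxicity table has no such line.

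**4. Is the row consistent with its neighbours?** The next row (> 5 to < 10 × ULN, bilirubin < 2 × ULN) has the same default of continuing treatment, but directs that atezolizumab be withheld for suspected immune-mediated events. The restart bullet in the row at issue also presupposes that atezolizumab has been withheld.

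**5. How many rows?** Appendix 10, Table 2 has five AST/ALT rows: one continues both drugs (up to 3 × ULN), one makes withholding optional (the row at issue), and three withhold or stop (> 5 to < 10 × ULN if immune-mediated; > 3 × ULN with bilirubin > 2 × ULN; > 10 × ULN). 1 + 1 + 3 = 5, so the optional wording is in 1 of 5. The documents give no rate for this event, so no patient or missed-dose count follows.

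**The case against.** The strongest reply is that Appendix 10 is the specific guide and should govern. It is the one titled for Arm A and written for the combination, and Section 5.1 tells sites to follow arm-specific guidance. That is a natural reading but not a settled one. Atezolizumab is given only in Arm A, so Appendix 11 is Arm A guidance too, and Section 5.1.5.3 names it under an Arm A heading.

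A second reply is that the softer wording is deliberate. A rise in this range may come from cobimetinib: in the Phase III study with vemurafenib described in Section 5.1.1.2.1, Grade ≥ 3 liver abnormalities were 20.5% with cobimetinib and 15.1% without. It may also come from liver metastases, since Section 4.1.1.2 then admits patients with AST and ALT up to 5 × ULN. A patient who entered at 4 × ULN would have to fall below the entry value to restart. This stands as a cost. It is limited because the bullet applies only once immune mediation is suspected and the event has lasted more than 5 days, and because the row's 12-week stop already requires Grade 1.

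General text also softens the contrast. Appendix 11 says that atezolizumab may be suspended for related toxicity, and Section 4.4.3.1 leaves steroids to the investigator. Neither reconciles the two specific instructions.

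Safeguards exist: weekly liver tests, the pre-dose laboratory check (Section 4.5), 24-hour reporting of hepatitis and significant liver toxicity (Section 5.2.3), documented approval by the investigator and the Medical Monitor before rechallenge (footnote c), and the 12-week stop of both drugs. On non-resolution Appendix 10 is the stricter of the two. These make the point minor; they do not remove it.

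**Conclusion.** The inconsistency is real but small: optional against directed withholding of atezolizumab, in one row of five, with no rule of precedence. It rests on two things: the row's own implication that the event is above Grade 1, and Appendix 11's instruction for Grade 2 events of more than 5 days.

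A reader might infer that Appendix 11 requires permanent discontinuation for this patient. The documents do not support that. Its stop instruction needs Grade 3 or 4, or a Grade 2 event that fails to resolve. Nothing printed shows that > 3 to < 5 × ULN reaches Grade 3, and for non-resolution Appendix 10 also stops treatment. Nor do the documents show that Appendix 11 outranks Appendix 10 in general.

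SAP Section 2.5 announces early termination, which limits the remaining exposure. Alpha, power and the primary endpoint are not affected. It is worth correcting as a cheap safety improvement.

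**What to change.** In that one row of Appendix 10, Table 2, replace "Consider withholding atezolizumab" with *Withhold atezolizumab*, keeping footnote c. This matches the next row. Leave the cobimetinib instruction and the steroid, restart and 12-week bullets as they are.

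Do not add a cross-reference to Appendix 11 in this row, because that table directs prednisone and the row leaves it optional. Do not add a general sentence giving Appendix 11 priority either. It would also change the handling of tolerable Grade 2 diarrhea, steroids in Grade 2 pneumonitis, and the > 5 to < 10 × ULN row.

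The cost is one bullet, with no new data, visits or patients, plus some extra atezolizumab interruptions in patients whose rise later proves due to cobimetinib or liver metastases. Their number cannot be estimated from the documents. The change does not resolve the steroid difference. Nor does it resolve the separate difference in the > 5 to < 10 × ULN row, where Appendix 10 withholds and Appendix 11 would stop atezolizumab if the event is Grade 3 or 4.
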